# APPLICATION & PROTOCOL

Summary of sample analyses for Brussels sprouts and DIM cycles							
Time point	DIM blood	DIM urine	Estrogen blood	Estrogen urine	14C-BaP blood	14C-BaP urine	Background PAH blood
-7 days	x	x	x	x			x
0	x	x	x	x	x	x	x
0.25 – 24 hours	x	x			x	x pooled	
48 hours	x	X 24-48 hr pool	x	X 24-48 hr pool	x	x 24-48 hr pool	

**1** If the study involves accessing student education records, list all data to be used (e.g. course grades, assignments, GPA, video-recordings of class activities, etc.)

**1** Identify any surveys or questionnaires that are being tested or validated instruments that have been modified for the purposes of this study.

**1** Identify any novel or modified experimental activities that are being tested the purposes of this study.

**1** Specific information related to the use of drugs, devices, biologics, food, biospecimens, and radiation will be requested later in this document.

2 If any of the activities would be conducted regardless of the research, briefly describe those activities here:

**1** **Example:** Grant is funding the expansion of an existing training program. Research will be conducted to compare outcomes between participants from the original program and those participating in the expanded program. In this scenario, the program would be administered regardless of the research question and should be briefly described in this section.

3 Describe the qualifications that study team members possess to safely and appropriately conduct the study activities:

**1** [name], PhD in Biochemistry, is a Toxicologist with over 40 years of experience working with Polycyclic Aromatic Hydrocarbons (PAHs) and has directed similar human studies involving micro-dosing of PAHs at OSU.

[name], RN, the Clinical Research Nurse Coordinator (nurse coordinator) has extensive experience in

## APPLICATION & PROTOCOL

clinical research coordination, laboratory research, science communication for the lay public, and project management. In addition to being a registered nurse, [name] has completed a certified phlebotomy training course, intravenous therapy training, and a clinical research coordinator (CRC) training course.
 
[name] has performed carcinogen and radioisotope handling over the course of 32 years, including 15 years with the study PI. [name] is trained and approved to handle extreme carcinogens and participates in OSU's medical surveillance program. As the person in charge of the LPI extreme carcinogen facility it is her responsibility to dilute extreme carcinogens such as benzo[a]pyrene to concentrations considered safe for handling per the OSU EHS guidelines. [name] also maintains chemical and ionizing isotope inventories. [name] is trained in proper shipping and handling of biological and hazardous materials. For this protocol, [name] will perform handling of extreme carcinogens, dilute carcinogen solutions as well as BaP capsule preparation. [name] was trained to carry out the capsule preparation protocol by [name], a former graduate student in the [name] lab and person responsible for capsule preparation on previous IRBs. [name] was a pharmacy technician before entering graduate school. The training first entailed observing [name] prepare capsules for several cycles. Under [name]'s guidance [name] prepared a set of capsules. Capsules were evaluated for the proper level of C-BaP with liquid scintillation counting. This was repeated over several weeks to ensure consistency over time.
			
4	Will participants be audio or video recorded for research purposes?		
5	If "yes", indicate whether being recorded is required in order to participate and explain this in the consent document or guide:		
			
6	Does the study involve conducting research activities online?		
7	Is the study designed to be implemented in phases, where fully describing one phase is dependent upon the outcome of another?		
	IRB approval must be obtained prior to initiating each phase.		
SECTION 21 - Compensation		Yes	No
1	Describe any compensation or incentives for participants:		
	Subjects will receive \$125 for the BaP-only cycle and \$150 each for the DIM and Brussels sprouts cycles for a total of \$425 for the 3 cycles or \$300 if only doing the DIM and Brussels sprouts cycles. Subjects who		

# APPLICATION & PROTOCOL

discontinue the study early will be paid an amount pro-rated to the percentage of total blood samples completed. The amount will be determined by multiplying the number of study blood samples completed by \$11.36.
 
Subjects also receive up to \$10 worth of breakfast foods and beverages on day 1 of each cycle.
						
	
Include details concerning the conditions under which research participants would receive partial payment or no payment at all (e.g., withdrawing early from the study)
					
SECTION 22 - Costs				Yes	No	N/A
1	Describe any costs to participants that are associated with the study (e.g., parking, travel, etc.):					
	Subjects are responsible for transportation to and from the study site. A parking space outside of LPSC is reserved for study subjects during their visits.					
	
This section should not include costs incurred by the study team or the study.
					
SECTION 23 - Education Records				Yes	No	N/A
	
Education Record is defined by FERPA as a range of information about a student that is maintained in schools in any recorded way, such as handwriting, print, computer media, video or audio tape, film, microfilm, and microfiche.
					
1	Does the study involve the use of student education records?					
1a	If yes, list all data to be used (e.g. course grades, assignments, GPA, video-recordings of class activities, etc.):					
						
2	Are any of the education records related to OSU students?					
3	How will education records will be accessed or obtained (e.g., provided by class instructor; request will be submitted to the Office of the Registrar; etc.)?					
						
	
Information on Feasibility Determinations and Data Requests through the Office of the Registrar
					

# APPLICATION & PROTOCOL

SECTION 24 - Drugs or Biologics		Yes	No	N/A
	Guidance and decision trees on Drugs, Biologics, and Dietary Supplements			
1	Are one or more drugs or biologics being studied as part of this project?			Skip to section 25
2	Drug Name (include generic and trade name, if applicable):			
	 [7-  C]-benzo[ a ]pyrene (BaP), specific activity 27 µCi/µmol			
3	Approval Status (e.g., FDA Approved, FDA Approved/Unapproved Use, not FDA approved):			
	 not approved for therapeutic use; this protocol is an amendment to FDA IND 117175 (see IRB Protocol 8233 for FDA correspondence)			
4	Has an IND application been submitted to the FDA?			
5	If no, provide justification:			
				
6	Chemical formula:			
	 C 20 H 12			
7	Dosage strength(s):			
	 50 ng			
8	Rationale for choosing the drug or substance dose:			
		The impact of diet and/or supplements on the pharmacokinetics of a PAH when an individual is exposed to an environmentally relevant defined dose has never been determined. This information will be very useful to regulatory agencies in order to incorporate this important variable into the risk assessment models for PAH mixtures that utilizes the Relative Potency Factor (RPF) approach, derived from animal studies  . BaP is the reference compound and has an RPF of 1. The accuracy of the RPF approach is based on the assumption that the interaction between all PAHs is additive (same Mechanism of Action or MOA) and that high-dose animal data (fed semi-synthetic defined diets) can model human exposure at environmentally relevant levels (orders of magnitude lower than the animal studies). If cruciferous vegetables and their		

## APPLICATION & PROTOCOL

	phytochemical components can impact the uptake, metabolism and/or elimination of BaP, this will have a significant impact on the validity of the RPF approach. DIM is an OTC commercially available and common supplement which has GRAS status. This study is intended to evaluate the effect on structure or function of the body (rate of metabolism and elimination of micro-doses of [  C]-BaP).		
9	Method/route of administration:		
 9	oral in a food-grade cellulose capsule		
10	Mechanism of action:		
 10	BaP is not a therapeutic, so the mechanism of action described involves the current understanding of BaP carcinogenesis. The most well accepted mechanism for BaP carcinogenesis involves metabolic activation  . Bioactivation to the ultimate carcinogen is initiated by epoxidation at the 7,8-position. The epoxide is hydrolyzed by the action of the enzyme epoxide hydrolase and a second epoxidation produces the ultimate mutagenic and carcinogenic metabolite, the BaP-7,8-dihydrodiol-9,10-epoxide. The (+)-anti-BaP-7,8-dihydrodiol-9,10-epoxide metabolite is the most mutagenic and carcinogenic form of BaP. The metabolite is formed by oxidative metabolism by cytochrome P450 enzymes (CYPs) enzymes, primarily in the liver (also to some degree in lung and GI). The epoxide is chemically unstable and has been shown to react with the N  position in guanine in DNA which can lead to mutations in genome sequence. To date we have not detected any of this [  C]-BaP metabolite (or tetrol hydrolysis products) by UPLC-AMS in plasma or any covalent DNA adducts in PMBCs.		
11	Known drug interactions:		
 11	Not applicable at this microdose		
12	Manufacturer/Sponsor:		
 12	American Radiolabeled Inc. (ARC, custom synthesis)		
13	Manufacturer/Sponsor Location:		
 13	St. Louis, Missouri		
 14	If manufactured on site at OSU, provide details of facilities and restricted access.		
14	Name of supplier:		
 14	Same as Manufacturer (custom synthesis)		

## APPLICATION & PROTOCOL

15	
Summarize preclinical and early human studies (for studies that are required to have an investigational new drug (IND) number):
 
BaP is one of the most extensively studied PAH environmental contaminants. BaP is a skin carcinogen in the rodent 2-stage model involving dermal application and promotion by TPA. In addition to dermal exposures, BaP has been documented as an animal carcinogen following oral or inhalation exposures. Target tissues include liver, forestomach, esophagus, auditory canal and oral cavity. Occupational exposures in humans are associated with increased incidences of cancers of the lung, skin and bladder.
 
Animal studies in mouse and rat confirm the carcinogenic potential of BaP when administered by the oral route, a mimic of human exposure. Dose-dependent appearance of tumors can be observed in the forestomach, esophagus, tongue and larynx in a somewhat reliable manner. A summary of animal studies in which BaP was administered by the oral route is provided in the table below, the dose information was converted to mg/kg for ease of comparison. The summary only includes studies which evaluated untreated control animals as a negative control.
 
Animal Studies with Orally Administered Benzo[a]pyrene
 																									
	
  
 Species	Dose (mg/kg)	Route; Regimen	Duration	Tumor Observations	Reference (all in Ref 2)	
   
 Mouse, A/J	0 550 3,350	Oral, Diet	260 days	Forestomach tumors 0/21 (0%) 5/25 (20%) 27/27 (100%)	Weyand et al., 1995 Chem Res Toxicol 8(7): 949-954	
 
 Mouse, B6C3F1	0 5 25 100	Oral, Diet	2 years	Forestomach tumors 1/48 (2%) 3/47 (6%) 36/46 (78%) 46/47 (98%)	Culp et al., 1998 Carcinogenesis 19(1): 117-124	
 
 Mouse, Swiss	0 50	Oral 2X/week, 4 weeks	27 weeks	Forestomach tumors 0/10 (0%) 10/10 (100%)	Badary et al., 1999 Eur J Canc Prev. 85 435-440	
  
	Species	Dose (mg/kg)	Route; Regimen	Duration	Tumor Observations	Reference (all in Ref 2)	Mouse, A/J	0 550 3,350	Oral, Diet	260 days	Forestomach tumors 0/21 (0%) 5/25 (20%) 27/27 (100%)	Weyand et al., 1995 Chem Res Toxicol 8(7): 949-954	Mouse, B6C3F1	0 5 25 100	Oral, Diet	2 years	Forestomach tumors 1/48 (2%) 3/47 (6%) 36/46 (78%) 46/47 (98%)	Culp et al., 1998 Carcinogenesis 19(1): 117-124	Mouse, Swiss	0 50	Oral 2X/week, 4 weeks	27 weeks	Forestomach tumors 0/10 (0%) 10/10 (100%)	Badary et al., 1999 Eur J Canc Prev. 85 435-440	
Species	Dose (mg/kg)	Route; Regimen	Duration	Tumor Observations	Reference (all in Ref 2)																					
Mouse, A/J	0 550 3,350	Oral, Diet	260 days	Forestomach tumors 0/21 (0%) 5/25 (20%) 27/27 (100%)	Weyand et al., 1995 Chem Res Toxicol 8(7): 949-954																					
Mouse, B6C3F1	0 5 25 100	Oral, Diet	2 years	Forestomach tumors 1/48 (2%) 3/47 (6%) 36/46 (78%) 46/47 (98%)	Culp et al., 1998 Carcinogenesis 19(1): 117-124																					
Mouse, Swiss	0 50	Oral 2X/week, 4 weeks	27 weeks	Forestomach tumors 0/10 (0%) 10/10 (100%)	Badary et al., 1999 Eur J Canc Prev. 85 435-440																					

## APPLICATION & PROTOCOL

	Mouse, Muta	0 75 125	Oral, 5 consec. days	41 weeks	Forestomach tumors 0/8 (0%) 10/10 (100%) 10/10 (100%)	Hakura et al., 1998 Regul Toxicol Pharmacol 27(3): 273-279		
	Rat, Sprague Dawley	0 6 39	Oral, 1x/9 days 5X/week	Lifespan	Combined tumors 3/64 (4.7%) 3/64 (4.7%) 10/64 (15.6%)	Brune et al., 1981 J Canc Res Clin Oncol 102(2): 153-157		
	Rat Crl:CD	0 63	Oral, 1x/week 8 weeks	49 weeks	Mammary Tumors 1/30 (3%) 11/30 (37%)	El-Bayoumy et al.,1995 Carcinogenesis 16(2):431-434		

The mouse study of Culp et al., 1998 (see above Table) utilized the lowest exposure with 5 mg/kg (a dose 100,000 times greater than the dose in our microdose studies) which did not produce a significant increase in tumor incidence. This is similar to the rat study of Brune et al., 1981 (see above Table) in which a dose of 6 mg/kg did not result in an increase in tumors when animals were monitored for their lifetime.
								
16	Will an FDA-approved drug be administered for an indication, dose, route of administration, or subject population that is different from what has been approved for the marketed product? If "yes", explain and provide justification and safety information:							
17	
 Provide the plan for the storage, dispensing, handling, inventory control, and disposal of investigational, FDA-approved drugs, and/or biologics:
 
 Preparation Location: The lab where the capsules are prepared (LPSC 383) is not a radiopharmacy. Because these capsules are created solely for the purposes of this study and are not to be considered a therapeutic drug, they are not made to GMP standards but will be prepared with the highest quality, consistency and precision possible. Room 383 is a locked, secure laboratory, and no other activities occur in this space besides those related to BaP handling and capsule preparation. [name] and [name] are the only persons with keys to access this space.
							

## APPLICATION & PROTOCOL

Capsules intended for human use will be prepared in a clean hood dedicated solely to capsule preparation. Concentrated  $^{14}\text{C}$ -BaP stock solution is not diluted in the same area as capsule preparation. The hood where capsule preparation is performed will be surveyed for radioactivity by taking swipes and evaluating with liquid scintillation counting. The capsule preparation hood will be sterilized with bleach and alcohol, and all work surfaces will be covered with fresh, plastic backed laboratory bench paper. All pipettes are calibrated, dedicated to this procedure, and only used with sterile, filter pipette tips. All Hamilton syringes were purchased new, checked for accuracy, and dedicated to this project.

*Material storage & preparation:* Prior to use, empty Solaray® capsules and pharmaceutical grade lactose monohydrate NF (Spectrum Chemical Mfg. #61-1730890) are stored in an airtight bag in a gasket sealed plastic box, in a cabinet in a lab that does not utilize scintillation-detectable radioactivity or human tissues. This box contains all microdosing supplies in an area separated from traditional laboratory supplies.

The  $^{14}\text{C}$ -BaP is shipped as a concentrated solution (0.10 mCi/mL; specific activity = 27 nCi  $^{14}\text{C}$ /nmol BaP = 0.103 nCi/ng) in toluene. This concentrated solution is stored in sealed containers as received from the supplier at -80°C in a secure carcinogen laboratory in LPSC 383. In order to ensure radiochemical purity (greater than or equal to 98% for the purified concentrated stock) and to prepare a diluted sample suitable for human consumption, the compound is collected as a single peak from an HPLC run. The identity of the compound is confirmed by co-elution with a non-radioactive standard.

A working stock solution will be prepared by diluting the 0.10 mCi/mL  $^{14}\text{C}$ -BaP concentrated solution. The stock solution will contain 50 ng  $^{14}\text{C}$ -BaP /25  $\mu\text{L}$  = 2 ng/ $\mu\text{L}$  (5.4 nCi  $^{14}\text{C}$ /25  $\mu\text{L}$  = 0.2 nCi/ $\mu\text{L}$ ). For example, to make 4 mL of stock solution, 8  $\mu\text{L}$  of the 0.10 mCi/mL solution will be aliquoted into a clean vessel. Toluene is carefully evaporated off, and the  $^{14}\text{C}$ -BaP aliquot resolubilized into 4 mL 95% food grade ethanol. The radioactivity will be checked with a liquid scintillation counter and adjusted to the target concentration if needed.

The stock solution will be aliquoted into clean 2 mL amber glass vials and stored under argon at -80°C. Each stock solution is checked for  $\geq 95\%$   $^{14}\text{C}$ -BaP radioisotope purity on a quarterly schedule throughout the study. Stock solutions will be checked for both purity and concentration on UPLC using UV detection for BaP and radioisotope detection for  $^{14}\text{C}$ .

*Capsule preparation, verification and storage:* [name] and [name] have been trained to prepare the capsules. As an added safety measure, a second trained study team member will also be present during capsule preparation for quality control to verify capsules are produced per specified SOPs.

Each capsule will contain only the  $^{14}\text{C}$ -BaP and lactose as an excipient. Empty vegetarian capsules, size 0,

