## APPLICATION & PROTOCOL

as “microdosing” (Phase 0 studies or eIND studies). This approach has been validated for exploratory clinical development by the Consortium for Resourcing and Evaluating AMS Microdosing (CREAM Trial) and the EU Microdosing AMS Partnership Programme (EUMAPP). This early use of human subjects in drug development is consistent with the goals of the FDA Critical Path Initiative and AMS in exploratory IND applications has been addressed by FDA. AMS has been used in toxicology and carcinogenesis studies. AMS sensitivity allows the study of pharmacokinetics and DNA binding of environmental contaminants known to be animal carcinogens and suspected of being human carcinogens including the cooked meat mutagens PhIP and MelQx, the mycotoxin and human hepatocarcinogen aflatoxin B1 (AFB1), in addition to BaP. It is noteworthy that our group has successfully completed AMS studies with AFB1 and the PAH, dibenzo[def,p]chrysene (DBC). IARC estimates that a non-smoker, not exposed occupationally, will receive a daily dose of 270-700 ng of BaP; about 95% through the diet. The European Union maximum limit for BaP in fish is 2,000 ng/Kg f.w. and the FDA Limit of Concern (LOC) is 35,000 ng/Kg. The dose of 50 ng would be the equivalent of eating 25 or 1.4 g of fish at the EU, and FDA limits, respectively. The World Health Organization has set an estimated safe daily lifetime (70 years for a 70 Kg individual, cancer endpoint) exposure to BaP of 42-350 ng. With respect to the internal dose of [C] of 5.4 nCi, this represents 0.6% the dose given in a common diagnostic procedure (C-urea test for Helicobacter) and 4 to 5 orders of magnitude lower than a recently published paper dosing people with 300 µCi of epicatechin. Therefore, from the standpoint of both chemical and radioisotope dose to the volunteers, this protocol represents de minimus risk and that was the finding of the FDA (IND 117175) in a “study may proceed” determination for our current study (IRB protocol 5644) which uses a dose of 46 ng (5 nCi).

	Provide survey questions, questionnaires, interview and focus group guides, references/citations, etc., as separate attachments.			
2	Provide details of where data will be collected. Examples: Online, OSU campus, K-12 classrooms, U.S. parks, senior living communities in Denmark.			

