## APPLICATION & PROTOCOL

composed of vegetable cellulose, will be opened and held in a microtube rack. The empty capsules will be filled with lactose. The 25 µL aliquot of either stock solution will be applied to the lactose with a calibrated pipet fitted with a sterile filter tip. The ethanol is allowed to evaporate, and then the capsules are sealed with their caps.

Five (5) capsules will be prepared in each batch: Up to two (2) subjects may participate in a study cycle per week and three (3) capsules will be used for quality control verification.

Capsules for quality control: Immediately after preparation, 3 of the 5 capsules will each be dissolved in 5 ml ultrapure water and 15 ml scintillation cocktail and counted on a liquid scintillation counter. Results will be emailed directly to the director of OSU Radiation Safety (RSO). Once the RSO has determined that the three evaluated capsules are within 10% variance and 10% error, the results are emailed to [name] or [name]. [name] will then contact [name] and [name] that the cycle(s) may proceed. If the capsules are not given RSO approval, a new set of capsules will be prepared and the subject(s) will be rescheduled if needed.

Capsules for subjects: Two capsules will be stored in sealed vials in the dark in a zipper-lock plastic bag with silica desiccant at -20°C until subject consumption. The bag will be labeled appropriately (see sample label). Any capsules not used within 1 week will be discarded.

*Dispensing:* Capsules will be transported to the Clinical Research Center (407 LPSC) in sealed vials within the labeled zipper-lock plastic bag. The bag will be stored within a plastic box for transportation to the clinic.

One (1) capsule containing 50 ng [C]-BaP will be administered to the subject with 100 mL of water by the nurse coordinator at the start of the study cycle.

*Inventory control:* Information including number of capsules, date of preparation, and operator are recorded immediately after capsules are prepared. Date of consumption and disposal of test capsules are recorded on day 1 of the cycle. If test capsules do not pass approval by the OSU radiation safety officer, the information is still recorded and a new set of capsules will be prepared.

*Disposal:* Capsules that are not needed, expired or rejected for human use will be disposed of in the radiochemical dry waste at Oregon State University.

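### Section 24 item 17: the worked dilution gives 5.0 nCi (about 46.7 ng) per 25 µL, not the stated 5.4 nCi / 50 ng; the specific activity per ng and the Section 37 total also need correcting

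*Combined protocol and SAP*

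**What the plan says.** All references are to the combined protocol and SAP.

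- **Dose.** Section 24, item 7 gives 50 ng, and item 17 repeats it at dispensing: "One (1) capsule containing 50 ng". Section 13, item 1 gives the activity: "of 5.4 nCi, this represents 0.6% the dose given in a common diagnostic procedure". Section 28, item 7b gives the same activity as 0.0000054 mCi.
- **Working stock (Section 24, item 17).** The target is 50 ng per 25 µL, printed as 2 ng/µL, and 5.4 nCi per 25 µL, printed as 0.2 nCi/µL. The specific activity is 27 nCi/nmol, converted in the text as "nmol BaP = 0.103 nCi/ng".
- **Worked dilution (same paragraph).** "For example, to make 4 mL of stock solution, 8" µL of the 0.10 mCi/mL solution is taken, the toluene is evaporated, and the residue is taken up in 4 mL of ethanol.
- **Later checks (same item).** "The radioactivity will be checked with a liquid scintillation counter and adjusted to the target concentration if needed". "Stock solutions will be checked for both purity and concentration on UPLC using UV detection for BaP", together with radioisotope detection. Capsules are released once "the three evaluated capsules are within 10% variance and 10% error".
- **Totals.** Section 37, item 3 gives 16.4 nCi for three cycles and 10.8 nCi for two.

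**The concern.** The paragraph that describes how the administered dose is made leads to two different doses. One is stated (5.4 nCi, 50 ng). The other follows from the example (5.0 nCi, about 46.7 ng). The target concentration is printed in rounded form, and that form agrees with the example rather than with 5.4 nCi. A technician comparing a count with 0.2 nCi/µL could therefore see no reason to adjust.

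What is at stake is the accuracy of the absolute dose. A constant shortfall cancels when the same person's cycles are compared. It cancels only if every cycle was prepared to the same target, though. Section 20 lets participants who completed a 50 ng BaP-only cycle under protocol 8233 or 8554 within the prior 12 months skip that cycle here, so for them the reference cycle comes from another protocol. The SAP also models pharmacokinetic parameters as a function of external dose, which makes the dose figure an input to the analysis.

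**Working it through.** **Inputs.** Concentrate 0.10 mCi/mL = 100 nCi/µL; example 8 µL into 4 mL (4,000 µL); capsule aliquot 25 µL; target 50 ng and 5.4 nCi per 25 µL; release tolerance 10% (all Section 24, item 17). Specific activity 27 nCi/nmol (items 2 and 17); formula C20H12 (item 6). With standard atomic masses the molar mass is 20 × 12.011 + 12 × 1.008 = 252.316 ng/nmol.

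**1. The stated dose reproduces.**
- 27 / 252.316 = 0.1070 nCi/ng.
- 50 ng × 0.1070 = 5.35 nCi, which rounds to 5.4.
- 50 / 25 = 2 ng/µL, as printed.
- 5.4 / 25 = 0.216 nCi/µL, printed as 0.2.

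**2. The worked dilution does not reproduce it.**
- 8 µL × 100 nCi/µL = 800 nCi.
- 800 / 4,000 = 0.200 nCi/µL; × 25 = 5.00 nCi.
- 5.00 / 0.1070 = 46.7 ng.
- Shortfall in activity: 1 − 5.00/5.4 = 7.4%. Shortfall in mass: 1 − 46.7/50 = 6.5%.

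**3. Other conversion factors do not rescue the mass.** The example gives 46.3 ng at 0.108 nCi/ng (the ratio 5.4/50), 47.1 ng if every molecule carries one 14C (254.308 g/mol), and 48.5 ng at the printed 0.103. All are below 50 ng.

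**4. Rounding of the inputs.** If 0.10 mCi/mL stands for 0.095 to 0.105, the example gives 4.75 to 5.25 nCi. If only the 8 µL is rounded (7.5 to 8.5), it gives 4.69 to 5.31 nCi. Only with both rounded does the range, 4.45 to 5.58 nCi, include 5.4.

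**5. The checks.** A 0.200 nCi/µL stock equals the printed 0.2 target. Taking 5.4 nCi as the reference, which is an assumption because the text names none, the 10% band is 4.86 to 5.94 nCi and contains 5.0.

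**6. The specific activity per ng.**
- The printed 0.103 needs a molar mass of 27 / 0.103 = 262.1 g/mol, which is not C20H12.
- Counting one 14C in every molecule gives 27 / 254.308 = 0.106.
- Reading 27 as rounded (26.5 to 27.5) gives 0.105 to 0.109. None of these reaches 0.103.
- With 0.103, 50 ng would be 5.15 nCi, not 5.4.

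**7. The Section 37 total.** 2 × 5.4 = 10.8, as printed. 3 × 5.4 = 16.2, against 16.4 printed (16.4/16.2 = 1.012, or +1.2%).

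**8. The replacement aliquot.** For 5.4 nCi: 0.216 × 4,000 / 100 = 8.64 µL. At 8.6 µL: 860 / 4,000 = 0.215 nCi/µL; × 25 = 5.38 nCi; / 0.1070 = 50.2 ng.

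**The case against.** The best defence is that the step is labelled an example, uses coarse figures, and is followed by three checks. The count is to be adjusted to target, and the same sentence that rounds to 0.2 nCi/µL also gives 5.4 nCi and 50 ng per 25 µL. The UPLC check measures BaP mass independently of activity, and would read 46.7/25 = 1.87 ng/µL against 2. The concentrate is also purified by HPLC, so the measured count rather than the nominal 8 µL may set the real concentration. Finally, 7.4% is within the plan's own 10% tolerance.

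Much of this stands, and it is why the point is minor. It does not make the printed figures agree. The adjustment step refers to a target concentration, and the activity concentration on the page is 0.2. Acceptance limits for the checks may sit in the SOPs or in the Protocol 8233 quality documents, which are not in hand, so no fault is claimed there.

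Three stronger readings go beyond the documents:

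- **That participants were given 5.0 nCi.** Nothing reports the content of any capsule, and the checks could have corrected the stock.
- **That the example was carried over from the earlier study,** "which uses a dose of 46 ng (5 nCi"). The figures resemble each other, but rounding 0.216 to 0.2 explains the example equally well and the text settles neither.
- **That capsule control would miss, or would catch, such a batch with some known probability.** No capsule-to-capsule variability is given, and the release rule can be read per capsule or on the mean.

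**Conclusion.** The point holds as an internal inconsistency in the dosing text. The worked dilution yields 5.0 nCi and about 46.7 ng per 25 µL, 7.4% and 6.5% below the stated 5.4 nCi / 50 ng. The stated dose is the sound figure, because it follows from 27 nCi/nmol and C20H12. The example, the rounded 0.2 nCi/µL and the 0.103 nCi/ng are the outliers. The 16.4 nCi in Section 37 is a separate 1.2% slip.

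The activity result takes 0.10 mCi/mL and 8 µL at face value; the mass result also takes 27 nCi/nmol and standard atomic masses. It would disappear only if both the concentrate strength and the aliquot were rounded down from larger values.

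Severity is minor. The direction is under-dosing, which adds no safety risk, and a constant error cancels in comparisons between cycles prepared to the same target. The stated pair of 5.4 nCi and 50 ng was evidently not computed from 0.103, so no downstream effect of that misprint is visible in the documents.

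**What to change.** Keep 5.4 nCi / 50 ng as the single stated dose and bring the other figures into line with it.

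In Section 24, item 17:
- print the target as about 0.216 nCi/µL (2 ng/µL) in place of 0.2;
- change the example aliquot from 8 to about 8.6 µL per 4 mL (about 5.4 nCi and 50 ng per 25 µL);
- print the specific activity as 0.107 nCi/ng in place of 0.103.

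In Section 37, item 3, change 16.4 to 16.2 nCi.

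The cost is four figures in the text. No procedure, sample, visit or analysis changes. The laboratory should confirm at the same time that its SOP uses the corrected target.
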